7.4.2 Permitted Therapies

Patients will be permitted to use all regular medications that are not explicitly excluded by the protocol (see Section 7.4.1). Additionally, patients are permitted to use NSAIDs, SNRIs, acetaminophen (paracetamol), and mild opioid analgesic during the course of the study, as long as their dosing is stable at least 4 weeks prior to Screening and during the study period. Any variance from this stable dosing regimen will be recorded in the eCRF Concomitant Medication Log. Variation of NSAID or other analgesic use could impact the interpretation of patient-reported outcomes of pain and function during the course of the study. If it becomes clinically necessary to treat worsening of OA symptoms during the study, it is preferable to adjust medications in the existing regimen over prescribing new analgesic or anti-inflammatory medications.

The use of topical or subcutaneous lidocaine or ethyl chloride topical spray during the IA administration procedure is permitted.

Patients who are taking prophylactic low-dose aspirin prior to Screening may continue on their regular regimen of this therapy during the Screening and the study period.

Patients who are taking metformin concomitantly should be maintained on a stable regimen during the study, as there is some evidence that metformin has beneficial effects on OA (Mohammed et al. 2014; Wang et al. 2019).

Permitted alternative and non-pharmacological therapies include the following:

- Nutritional supplements are permitted if they were a part of the patient's established regimen at least 6 weeks prior to Screening and the patient is committing to maintaining a consistent regimen during the study. Nutritional supplements taken must be recorded in the Concomitant Medication Log.
- Heat and cold therapy: Patients are permitted to use their usual practice of heat and cold therapy, but any variance from usual practice should be recorded in the Concomitant Medication Log.

Assistive devices are permitted during the study, provided the following are observed:

- The use of assistive devices at baseline will be recorded in the electronic data capture (EDC).
- Any change in the use of assistive devices during the course of the study will be recorded in the EDC as a measure of change.

8 SAFETY MONITORING

8.1 Definitions

- **AE**: An AE is any untoward medical occurrence associated with the use of an intervention in humans whether or not it is considered intervention related.
- Suspected unexpected serious adverse reaction (SUSAR): A serious AR that is unexpected based on current product information.
- **SAE**: An event is considered "serious" if, in the view of either the Investigator or the Sponsor, it results in any of the following outcomes:
 - Death
 - A life-threatening AE (An event is considered "life-threatening" if, in the view of either the Investigator or Sponsor, its occurrence places the patient at immediate risk of death. It does not include an AE or suspected AR that, had it occurred in a more severe form, might have caused death.)
 - Inpatient hospitalization or prolongation of existing hospitalization
 - A persistent or significant incapacity or substantial disruption of the ability to conduct normal life functions
 - A congenital anomaly/birth defect
 - Important medical events that may not result in death, be life-threatening, or require hospitalization may be considered serious when, based upon appropriate medical judgment, they may jeopardize the patient and may require medical or surgical intervention to prevent one of the outcomes listed in this definition. Examples of such medical events include allergic bronchospasm requiring intensive treatment in an emergency room or at home, blood dyscrasias or convulsions that do not result in inpatient hospitalization, or the development of drug dependency or drug abuse.
- Causality or relatedness: AEs should be considered probably or possibly treatmentrelated, unless they fulfill the following criteria (in which circumstances it should be considered unlikely related or unrelated):
 - Evidence exists that the AE has an etiology other than the Study Drug (e.g., preexisting medical condition, underlying disease, intercurrent illness, or concomitant medication), and/or
 - The AE has no plausible temporal relationship to administration of the Study Drug (e.g., a new cancer diagnosed 2 days after first dose of Study Drug).

Relatedness to Study Drug will be graded as "probably", "possibly", "unlikely", or "unrelated" as follows:

Probably related: The AE

- Follows a reasonable temporal sequence from drug administration
- Abates upon discontinuation of the drug
- Cannot be reasonably explained by the known characteristics of the patient's clinical state

Possibly related: The AE

- Follows a reasonable temporal sequence from drug administration
- Could have been produced by the patient's clinical state or by other modes of therapy administered to the patient

Unlikely related: The AE

 Is most likely to be explained by the patient's clinical state or by other modes of therapy administered to the patient

Unrelated: The AE

- Does not follow a reasonable sequence from drug administration
- Is readily explained by and considered by the Investigator to be an expected complication of the patient's clinical state, concurrent medical conditions, or by other modes of therapy administered to the patient
- AR: An AR is any AE caused by a drug.
- Suspected adverse reaction (SAR): An SAR is any AE for which there is a reasonable possibility that the drug caused the AE. For the purposes of the investigational new drug (IND) safety reporting, "reasonable possibility" means there is evidence to suggest a causal relationship between the drug and the AE. SAR implies a lesser degree of certainty about causality than AR.
- Unexpected: An event is considered unexpected if it is not listed in the IB, is not listed at the specificity or severity that has been observed, or, if an IB is not required or available, is not consistent with the risk information described in the General Investigational Plan or elsewhere in the IND. Unexpected also refers to events that are mentioned in the IB as occurring with a class of drugs or as anticipated from the pharmacological properties of the drug but are not specifically mentioned as occurring with the particular drug under investigation.
- Severity or intensity: The severity of an event describes the degree of impact upon the patient and/or the need for medical care necessary to treat the event. AEs reported for patients participating in this study will be graded using the National Cancer Institute Common Terminology Criteria for Adverse Events version 4.03 (NCI CTCAE v4.03). The Investigator will grade the severity of each AE using, when applicable, the NCI CTCAE v4.03. For AEs not included in the NCI CTCAE v4.03, the criteria outlined in Table 3 should be used as a general guideline.

Table 3 Grading for Adverse Events Not Covered in the NCI CTCAE

Severity	Description
Grade 1 – Mild	Asymptomatic or mild symptoms; clinical or diagnostic observations only; intervention not indicated
Grade 2 – Moderate	Minimal, local or noninvasive intervention indicated; limited age- appropriate instrumental ADL
Grade 3 – Severe	Medically significant but not life-threatening; hospitalization or prolongation of hospitalization indicated; disabling; limiting self-care ADL.
Grade 4 – Life- threatening	Life-threatening consequences; urgent intervention indicated
Grade 5 – Fatal	Death

ADL=Activities of daily living; NCI CTCAE=National Cancer Institute Common Terminology Criteria for Adverse Events.

8.2 Documenting Adverse Events

8.2.1 Timeframe for Collection

AEs and SAEs will be collected from the time of randomization and treatment. All events prior to this will be documented as medical history.

The Investigator must follow up on all AEs through Week 24 or the last study visit if the patient withdraws early. Nonserious AEs may be followed to resolution past the patient's last study visit at the discretion of the Investigator and/or Medical Monitor if in the best interest of the patient and the assessment of safety of UBX0101. The Investigator must follow up on all SAEs until the events have subsided, returned to baseline, or, in case of permanent impairment, the condition stabilizes.

8.2.2 Classification of Events

Although AEs should be based on the signs or symptoms detected during the physical examination and on the clinical evaluation of the patient, a specific diagnosis should be reported as the AE whenever feasible. In addition to the information obtained from those sources, the patient should be asked the following nonspecific question: "How have you been feeling since your last visit?" Signs and symptoms should be recorded using standard medical terminology.

8.3 Reporting Adverse Events

All AEs and SAEs must be recorded on source documents and collected in the EDC. Any unanticipated risks to the patients must be reported by the Investigator promptly to the Sponsor and IRB/IEC.

All SAEs, whether or not deemed drug-related or expected, must be reported by the Investigator or qualified designee within 24 hours of first becoming aware of the event. The Investigator or qualified designee will enter the required information regarding the SAE into the appropriate module of the eCRF, which will automatically result in distribution of the information to the Sponsors Pharmacovigilance provider. If the eCRF system is temporarily unavailable, the event, including the Investigator-determined causality to study drug, should be reported via fax using an SAE form to the appropriate Sponsor or Pharmacovigilance contact. Upon return of the availability of EDC system, the SAE information must be entered on the SAE eCRF.

The Sponsor (or designee) will process and evaluate all SAEs as soon as the reports are received. For each SAE received, the Sponsor will make a determination as to whether the criteria for expedited reporting have been met. The Medical Monitor should also be contacted immediately for any fatal or life-threatening SAE that is considered possibly or probably related to Study Drug.

The Sponsor (or designee) is responsible for reporting relevant SAEs to the relevant regulatory authorities and participating Investigators, in accordance with Food and Drug Administration regulations 21 Code of Federal Regulations 312.32, International Conference on Harmonisation (ICH) Guidelines, European Clinical Trials Directive (Directive 2001/20/EC, and/or local regulatory requirements and monitoring the safety profile of the Study Drug. To meet this requirement, the Sponsor (or designee) may request additional information from the sites including, but not limited to, hospitalization records, discharge summaries, or autopsy reports. Any requests for such information should be addressed in a timely manner. Additionally, any SAE considered by an Investigator to be possibly or probably related to the Study Drug that is brought to the attention of the Investigator at any time outside of the time period specified for

cal Study Protocol UBX0101

SAE reporting also must be reported immediately to one of the individuals listed on the Sponsor contact information page.

Reporting of SAEs by the Investigator to the IRB or IEC will be done in accordance with the standard operation procedures and policies of the IRB/IEC. Adequate documentation must be maintained showing that the IRB/IEC was properly notified.

8.4 Adverse Events of Special Interest

No AEs of special interest have been identified for UBX0101.

8.5 Clinical Laboratory Findings

Clinical laboratory tests will include the analytes in Table 4. Patients should be in a seated or supine position during blood collection.

Table 4 Laboratory Parameters

ш	em	·~t	ᆈ	~	~ /	٠
		-	CH	c n	ıv	

- Hematocrit
- Hemoglobin
- Platelet count
- RBC count
- Mean corpuscular volume
- WBC count with differential

Serum Chemistry:

- Albumin
- Alkaline phosphatase
- Alanine aminotransferase
- · Aspartate aminotransferase
- Blood urea nitrogen
- Calcium
- Carbon dioxide
- Chloride
- Creatinine¹
- Globulin
- Glucose
- Hemoglobin A1c (Screening)²
- Human chorionic gonadotropin³
- Lactate dehydrogenase
- Phosphorus
- Potassium
- Sodium
- Total and direct bilirubin⁴
- Total cholesterol
- Total protein
- Hepatitis B, Hepatitis C, Human Immunodeficiency Virus serology (Screening Only)
- Urine Drug Screen (Screening Only)

CKD-EPI= Chronic Kidney Disease Epidemiology Collaboration; RBC=red blood cell; WBC=white blood cell

¹ Creatinine clearance will be calculated by the CKD-EPI method (Levey et al. 2009).

² Patients with type 2 diabetes mellitus; performed as a reflex

³ Serum human chorionic gonadotropin is required only for females who are of childbearing potential.

⁴ Direct bilirubin is only required if total bilirubin is above the upper limit of normal.

8.6 Pregnancy

Although not considered an SAE, cases of pregnancy exposure by parent to the Study Drug must be recorded, reported, and followed up as indicated for an SAE. After the patient has been enrolled in the study and received Study Drug by IA injection, the Investigator must report immediately (within 24 hours or next business day whichever is the shorter) any drug exposure during pregnancy to the Sponsor using the Sponsor-supplied Pregnancy Reporting Forms, using the same contact method for SAE reporting. Information about exposure in pregnancy encompasses the entire course of pregnancy and delivery and perinatal and neonatal outcomes, even if there were no abnormal findings. All reports of pregnancy must be followed for information about the course of the pregnancy and delivery, as well as the condition of the newborn. When the newborn is healthy, additional follow-up is not needed. Pregnancies occurring up to 12 weeks after administration of the Study Drug must be reported to the Investigator.

8.7 Overdose or Misuse

Although not considered an SAE, cases of overdose (e.g., a dose higher than that indicated in the protocol, with or without an AE) must be recorded, reported, and followed up as indicated for an SAE.

9 STATISTICAL ANALYSES

9.1 Hypothesis Testing

Building on the favorable clinical responses and safety results obtained during the Phase 1 study, this Phase 2 study is intended to assess the efficacy, safety, and tolerability of a single-dose IA administration of UBX0101 in moderate to severe painful established femoro-tibial OA.

The hypothesis attached to the primary endpoint of this Phase 2 study is that UBX0101, when given as a single IA injection, is related to clinically significant changes in WOMAC-A (pain) compared to a single IA injection of placebo out to 12 weeks post-dose. Nested in the analyses to prove or disprove this hypothesis are factors such as dose response, magnitude, and duration of effect.

9.1.1 Sample Size Determination

Each of the four arms of the Phase 2 design are planned to have approximately 45 patients per group. The target number of patients per group randomized and treated was chosen to facilitate 40 patients per group completers for the 12 week primary endpoint of WOMAC-A score assuming a 10% dropout rate. The sample size was calculated based on Phase 1 WOMAC-A effect size and variability as measured by the mean and standard deviation of the least square mean differences between the treated groups and placebo at Week 12.

In the Phase 1 study, which included five to six UBX0101-treated patients per arm, there was an observed WOMAC-A effect size compared to placebo ranging from 0.2 to 0.7 and a standard deviation ranging from 0.2 to 0.4 on the 0–4 item subscore.

The sample size estimation for Phase 2 was a result of assuming a power of 90% and an alpha of 0.10 for a two-sample, two-sided comparison with an effect size of 0.50 (treated versus placebo) on the WOMAC-A item score (0–4) least square mean at 12 weeks with an assumed standard deviation of 0.75 to account for increased variability in a larger sample size, greater number of sites, and broader patient population under study compared with the previous Phase 1 study.

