In terms of clinical responses, patients treated with single IA injections of UBX0101 had clinically meaningful and dose-dependent improvements in knee pain symptoms as measured by the average daily pain NRS (0–10 point scale) and the WOMAC-A (Likert scale, 0–4) at 12 weeks compared to those who received placebo treatment. In a prospectively defined analysis in which the placebo (n = 14), low dose combined 0.1 through 0.4 mg UBX0101 (n = 16), and high dose combined 1 through 4 mg UBX0101 (n = 18) groups were compared, the least squares (LS) mean of the change from baseline (CFBL) in NRS at Week 12 was significantly greater for the high dose UBX0101 group (-3.95, p < 0.01) compared to the placebo (-1.96) and low dose groups (-2.66, p = 0.42 versus placebo). Especially for the UBX0101 4 mg highest dose group, LS mean reductions from baseline in the NRS of 4 points and greater up to Week 12 suggested a large magnitude UBX0101 treatment effect. Similarly, pain reduction as measured by WOMAC-A was clinically meaningful and greater in the high dose UBX0101 group compared to the placebo and the low dose groups. For the higher doses, the pain responses appeared to be durable through 12 weeks. The improvements in pain NRS over time in Part A are presented in Figure 2.

[figure not shown]

Figure 2 NRS Weekly Least Squares Mean Change From Baseline to Week 12

CFBL=change from baseline; LS=least squares; NRS = numeric rating scale; SE=standard error.

Clinically meaningful, dose-dependent improvements in physical function as measured by the Western Ontario and McMaster Universities Osteoarthritis Index function subscale (WOMAC-C) were observed and were greater in UBX0101-treated patients compared to those who received placebo. Evaluation of Patient Global Impression of Change (PGIC) following UBX0101 treatment demonstrated a higher proportion of patients being "much improved" or "very much improved" versus placebo at 12 weeks (placebo = 42.9%, low doses of UBX0101 [0.1, 0.2, and 0.4 mg] = 50.0%, high doses of UBX0101 [1.0, 2.0, and 4.0 mg] = 61.1%).

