WOMAC-A Score as the Primary Endpoint

WOMAC-A is a well-established, validated instrument for measuring pain in knee and hip OA that has been commonly used as a primary or major secondary outcome in many OA clinical studies. WOMAC-A has content validity because it is a composite of five questions about different situations when knee OA pain may manifest itself. Analysis of the change from baseline in WOMAC-A in the Phase 1 study suggested a dose response with increasing doses of UBX0101.

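### Does the unclear Phase 1 standard deviation of 0.2 to 0.4 in section 9.1.1 undermine the planning SD of 0.75?

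*Combined protocol and SAP*

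**What the plan says.** Section 9.1.1 (Sample Size Determination) describes the Phase 1 variability "as measured by the mean and standard deviation of the least square mean differences between the treated groups and placebo at Week 12". It then reports, from a study "which included five to six UBX0101-treated patients per arm", observed differences from placebo of 0.2 to 0.7 and "a standard deviation ranging from 0.2 to 0.4 on the 0–4 item subscore". The calculation itself rests on "assuming a power of 90% and an alpha of 0.10 for a two-sample, two-sided comparison", a treated-versus-placebo difference of 0.50 on the item score, and "an assumed standard deviation of 0.75 to account for increased variability in a larger sample size, greater number of sites, and broader patient population". The target is 40 completers per arm at Week 12 and about 45 randomized, with 10% dropout.

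Section 2.1.3 gives 14 placebo patients in Part A of Phase 1, 16 in the three low-dose arms together and 18 in the three high-dose arms together. It reports no SD for WOMAC-A. Section 4.2 says of WOMAC-A that "it is a composite of five questions about different situations when knee OA pain may manifest itself".

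**The concern.** Section 9.1.1 calls 0.75 an increase over Phase 1 but does not identify the figure it was raised from. Its description of the Phase 1 variability sounds like the standard error of a difference between arm means. Its report of the range sounds like a patient-level SD on the 0 to 4 scale. The two are different quantities, and no step leads from either to 0.75.

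This seems to matter because 40 completers is the smallest number that gives 90% power at SD 0.75. If the true Phase 1 patient-level SD were already near or above 0.75, the claimed allowance for more sites and a broader population would not exist, and real power would fall short of 90%.

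**Working it through.** **The plan's own figure.** Inputs from section 9.1.1: difference 0.50, SD 0.75, two-sided alpha 0.10, power 90%.

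- Normal approximation: n = 2 × [0.75 × (1.645 + 1.282) / 0.50]² = 38.5, so 39 per arm.
- Noncentral t: power is 89.8% at n = 39 and 90.5% at n = 40, so 40 per arm.
- Dropout: 40 / (1 − 0.10) = 44.4, so 45 randomized.

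The stated 40 and 45 reproduce. The 0.2 to 0.4 range does not enter the calculation.

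**Slack above 0.75.** With n = 40, the largest SD that keeps 90% power is 0.757 by the t-test. This margin is small because n was chosen as the smallest number that works at 0.75. It says nothing about whether 0.75 is itself cautious. Any reserve has to lie inside 0.75, so the question is what Phase 1 implies.

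**Reading 1: patient-level SDs.** 0.75 / 0.4 = 1.9 and 0.75 / 0.2 = 3.75. The allowance is large.

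**Reading 2: standard errors of each dose-versus-placebo difference, with all 14 placebo patients as comparator.** Assume a common SD and no covariate adjustment. Then SD = SE / √(1/n_t + 1/14), where the root is 0.521 for n_t = 5 and 0.488 for n_t = 6.

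| SE | Implied SD (n_t = 5 / 6) | Power at 40 per arm |
|---|---|---|
| 0.2 | 0.38 / 0.41 | above 99% |
| 0.3 | 0.58 / 0.61 | about 98% |
| 0.316 (root mean square of 0.2 and 0.4) | 0.61 / 0.65 | 97.8% / 96.2% |
| 0.4 | 0.77 / 0.82 | 89.3% / 85.5% |

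Only the last row falls below 90%. It takes the largest standard error as if it held for every arm. But under the common SD that the conversion assumes, standard errors could differ between arms only through arm size, by a factor of 0.521 / 0.488 = 1.07. A range printed as 0.2 to 0.4 needs a factor of at least 0.35 / 0.25 = 1.4, even allowing for rounding. The model that produces the shortfall is therefore inconsistent with the range it starts from.

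**Reading 3: spread of the differences across doses.** Six values lying between 0.2 and 0.7 have their largest sample SD when three sit at each end: √(6/5) × 0.25 = 0.27, or √(6/5) × 0.30 = 0.33 with rounding. This would be one number rather than a range, and it cannot reach 0.4. The reading can be set aside.

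**Which of the first two fits the range better?** Arm sizes of 5 to 6 with totals of 16 and 18 give 5, 5, 6 and 6, 6, 6. I simulated sample SDs for six normal arms of these sizes with one common true SD. The median ratio of largest to smallest SD was 2.4, and 73% of runs gave a ratio of 2 or more. A two-fold range is therefore ordinary for patient-level SDs from arms this small. The range sits more easily with Reading 1 than with Reading 2.

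**The case for a change.** The best argument for a change is that a reader cannot verify the claim of extra allowance from the protocol. The description in section 9.1.1 does point towards a standard error. A patient-level SD of 0.2 also looks very small: on the mean of five items each scored 0 to 4, it equals one response step on one question (1/5 = 0.2). At the top of the standard-error reading the allowance disappears. The sponsor holds the Phase 1 data, so stating the patient-level SD would cost a few lines.

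The point about wording stands: the quantity is not clearly named, and no Phase 1 patient-level SD for WOMAC-A is given. The inference to a power risk does not stand. It needs the standard-error reading, the pooled placebo comparator and the extreme value of the range all at once, under a model that the range contradicts. An SD of 0.2 in an arm of five or six is small but not impossible. SDs from arms of that size are also imprecise, which supports setting the planning value by judgement above the Phase 1 figures, as the plan did.

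**Conclusion.** No change to the plan is needed. Section 9.1.1 states every input to the calculation, the 90% power at 40 completers is correct at SD 0.75, and 0.75 is presented as an assumption with reasons. It is 1.9 to 3.75 times the Phase 1 figure on the patient-level reading. On the standard-error reading with the ends of the range averaged, it is about 1.2 times (0.75 / 0.65 = 1.16 to 0.75 / 0.61 = 1.24), with power of 96% to 98%. Only the extreme of the standard-error reading puts the ratio below 1 (0.75 / 0.82 = 0.91), with power of 85.5%.

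These figures assume an unadjusted two-sample t-test, exactly 40 completers per arm, a true difference of 0.50 and, for the standard-error reading, equal variances with all 14 placebo patients as comparator.

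What remains is loose labelling of background data. Saying whether 0.2 to 0.4 is an SD or a standard error would help a reader, but it would leave the number of patients, the analysis, the stated power and the interpretation of the result as they are.

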2.1.2.2 Justification for Dosing Strategy

The UBX0101 dose regimens planned for evaluation in this study were selected based on results from the Phase 1 Study UBX0101-OAR-101 (NCT03513016), which included a first-in-human, single-ascending dose evaluation (Part A) to establish an appropriate UBX0101 dose followed by a 6-week safety follow-up to collect additional safety and tolerability data.

In Part A of the Phase 1 study, single IA doses of 0.1, 0.2, 0.4, 1.0, 2.0, and 4.0 mg UBX0101 were studied. Following 12 weeks of data collection, doses of 1.0, 2.0, and 4.0 mg resulted in clinically significant improvements in both pain and physical function compared to placebo treatment. The findings are consistent with predictions from the UBX0101 pharmacokinetic (PK) model incorporating in vivo data and estimated human equivalent synovial concentrations that doses of 1.0 mg and higher administered via IA injection may produce sufficient exposure in the knee to induce apoptosis of SnCs in joint tissue.

Single IA doses of 0.5, 2.0, and 4.0 mg UBX0101 will be evaluated in the Phase 2 study. The highest single IA doses of 2.0 and 4.0 mg UBX0101 were informed by Phase 1 results, which showed a clear separation of the 2.0 and 4.0 mg doses from placebo on measures of pain and physical function over the 12-week study period. These will be repeated in the Phase 2 study to confirm the results observed over 12 weeks in the Phase 1 study in a larger population. The lowest dose chosen to establish the minimal- to no-effect level, 0.5 mg UBX0101, is supported by the findings at doses of 0.1, 0.2, and 0.4 mg UBX0101 in Phase 1, suggesting minimal to no difference in WOMAC pain subscale (WOMAC-A) versus placebo but mixed results when comparing over the 12-week study period using the numeric rating scale (NRS) measure of daily pain. In addition, in the Phase 2 study, all IA doses, including placebo, will be standardized to an 8 mL injection volume.

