4 STUDY PLAN

4.1 Study Design

This is a randomized, double-blind, placebo-controlled, single-dose, parallel-group study to assess the efficacy, safety, and tolerability of a single-dose IA administration of UBX0101 in patients with moderate to severe painful knee OA. Approximately 180 patients will be randomized (1:1:1:1) to one of four treatment groups (approximately 45 patients per group), all administered by IA route at Week 0. The four treatment groups will be enrolled concurrently.

Group 1: Placebo

Group 2: UBX0101 0.5 mg

Group 3: UBX0101 2.0 mg

Group 4: UBX0101 4.0 mg

Approximately 40 patients per group are expected to complete the Week 12 visit, assuming a 10% dropout rate. Study Drug will be administered as a single 8 mL IA injection at Week 0, Day 1. The primary endpoint analysis will be the change from baseline to Week 12 of the WOMAC-A score in patients receiving a single 0.5, 2.0, or 4.0 mg dose of UBX0101 versus those receiving placebo.

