9.1.3 Analysis of Efficacy Endpoints

The change from baseline to Weeks 12 and 24 of the WOMAC-A, NRS, and WOMAC-C will be analyzed based on details provided in the Statistical Analysis Plan.

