9.3 Procedures for Reporting Changes to the Planned Analysis

Additional details regarding the planned analyses, and any changes to those analyses described in this protocol, will be provided in the Statistical Analysis Plan.

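### Must the protocol say which dose comparison the 90% power and alpha of 0.10 in Section 9.1.1 describe, given that 0.5 mg is also in the primary endpoint?

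*Combined protocol and SAP*

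**What the plan says.** Section 9.1.1 plans about 45 patients per group so that 40 reach Week 12 after 10% dropout. It gets there "assuming a power of 90% and an alpha of 0.10 for a two-sample, two-sided comparison with an effect size of 0.50" on the 0–4 WOMAC-A item score, with an assumed SD of 0.75. The comparison is active against placebo, and no dose is named.

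Section 4.1 defines the primary analysis as the Week 12 change in WOMAC-A "in patients receiving a single 0.5, 2.0, or 4.0 mg dose of UBX0101 versus those receiving placebo". Section 9.1 attaches one hypothesis, about UBX0101 as such, and adds: "Nested in the analyses to prove or disprove this hypothesis are factors such as dose response, magnitude, and duration of effect".

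Section 2.1.2.2 gives the doses different roles. The 2.0 and 4.0 mg doses are repeated because they separated from placebo in Phase 1. For the third it says: "The lowest dose chosen to establish the minimal- to no-effect level, 0.5 mg UBX0101". The support is Phase 1 data at 0.1 to 0.4 mg, "suggesting minimal to no difference in WOMAC pain subscale (WOMAC-A) versus placebo", although the same sentence reports mixed findings on the daily pain scale.

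For the efficacy analysis, Section 9.1.3 says the endpoints "will be analyzed based on details provided in the Statistical Analysis Plan". Section 9.3 likewise assigns to the SAP "Additional details regarding the planned analyses, and any changes to those analyses described in this protocol".

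**The concern.** A dose picked to show little or no effect should not also be expected to show a difference of 0.50, so the 90% cannot sensibly be read as the power of the 0.5 mg comparison. Yet that comparison stands in the primary endpoint on the same footing as the other two. The protocol text names no lead contrast, testing order or adjustment.

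Two things would be at stake. A reader could attach 90% power and 10% error to a primary claim that has neither. And if nothing fixed the contrast beforehand, the most flattering of several could be presented as the primary one after the data are seen.

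**Working it through.** **Inputs.** From Section 9.1.1: difference 0.50, SD 0.75, two-sided alpha 0.10 (critical value 1.645), power 90% (1.282), 40 completers per group, 10% dropout. Effects at 0.5 mg of 0, 0.10 and 0.20, and high-dose effects below 0.50, are assumptions made here, because Section 9.1.1 does not split its Phase 1 range of 0.2 to 0.7 by dose. Powers use the normal approximation and count results favouring the drug; exact t-based values are lower by at most about half a percentage point.

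**1. The plan's own figure.**
- n = 2 × (1.645 + 1.282)² × (0.75/0.50)² = 38.5, so 39 per group. The t-test version gives 39.2, so 40.
- 40/0.9 = 44.4, so 45 randomized.
- SE = 0.75 × √(2/40) = 0.1677. Power = Φ(0.50/0.1677 − 1.645) = Φ(1.336) = 90.9%, or 90.5% with the t distribution.

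Two-sided 0.05 would need 48 per group and one-sided 0.10 would need 30, so the stated inputs are the ones that were used. The plan's figure is right for one active arm against placebo.

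**2. The 0.5 mg comparison.** Same SE.
- Effect 0.10: Φ(0.596 − 1.645) = 14.7%.
- Effect 0.20: Φ(1.193 − 1.645) = 32.6% (32.4% with t).

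Alpha is still 0.10 for this comparison if it is the one named. Only the power changes.

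**3. Other readings of the primary endpoint**, with 2.0 and 4.0 mg both at 0.50:

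| Reading | Power |
|---|---|
| One high dose named in advance | 91% |
| Both high doses significant (simulated, shared placebo) | about 84% |
| Either high dose significant (simulated) | 97% |
| 2.0 and 4.0 mg pooled: SE = 0.75 × √(1/80 + 1/40) = 0.1452 | Φ(3.443 − 1.645) = 96% |
| All three pooled, 0.5 mg at 0: mean effect 0.333, SE = 0.75 × √(1/120 + 1/40) = 0.1369 | Φ(2.434 − 1.645) = 78% |
| All three significant, 0.5 mg at 0 (simulated) | 5% |

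**4. Error rate if every dose were tested unadjusted.** Comparisons that share one placebo arm of equal size have correlation 0.5. The chance of at least one false positive among k is 1 − ∫ φ(x) [Φ(1.645√2 + x) − Φ(−1.645√2 + x)]ᵏ dx. That gives 10.0% for k = 1, 17.6% for k = 2 and 23.6% for k = 3. Counting only results that favour the drug, the figures are 5.0%, 8.8% and 11.8%.

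**5. Would one contrast be clearly better?** Take 0.5 mg at 0 and let one high dose have 0.50 and the other 0.30. A trend test on dose rank has SE = 0.75 × √(5/40) = 0.2652.

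| Approach | 2.0 mg 0.50, 4.0 mg 0.30 | 2.0 mg 0.30, 4.0 mg 0.50 |
|---|---|---|
| Trend test | Φ(0.70/0.2652 − 1.645) = 84% | Φ(0.90/0.2652 − 1.645) = 96% |
| Fixed sequence, first test at 4.0 mg | Φ(0.30/0.1677 − 1.645) = 56% (55% with t) | 91% |
| 2.0 and 4.0 mg pooled | Φ(0.40/0.1452 − 1.645) = 87% (86% with t) | the same |

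A Dunnett adjustment over three doses gives about 82% for a dose at 0.50 and, unlike the trend test and the pooled contrast, supports a claim for a single dose. The order depends on the shape of the dose response, which the trial is meant to learn. Sections 2.1.3 and 4.2 report Phase 1 improvement rising with dose, so the right-hand column is at least as relevant as the left.

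**The case for a change.** The case for a change runs like this. Readings that all fit Section 4.1 have power from 5% to 97%, and nothing in the protocol says which one the 90% belongs to. It is natural to guess that a high dose was meant, but even then one named dose, either and both give 91%, 97% and 84%. Pooling is plausible too, since Phase 1 prospectively grouped its doses ("high dose combined 1 through 4 mg UBX0101 (n = 18) groups were compared", Section 2.1.3). Naming the contrast costs no patients and protects the result only if done before unblinding.

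Part of this stands. The protocol text does not name the contrast, and 90% should not be quoted for 0.5 mg. The rest is weaker. A two-sample calculation sized per group is a per-comparison statement as it is; only the dose is left open. The protocol never claims 90% for 0.5 mg or for all doses together. An effect of 0.50 at 0.5 mg is unlikely on the protocol's reasoning but not ruled out: the dose lies above the 0.1 to 0.4 mg levels cited, and those gave mixed results on daily pain. A low arm expected to do little is how a dose-ranging design finds the lower end of the curve. And the request comes down to confirming something that Sections 9.1.3 and 9.3 already place in the SAP.

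**Conclusion.** No change to the plan follows. No stated figure or rule is wrong: the sample size reproduces, its alpha is valid for any one comparison fixed in advance, and its power is valid for any dose whose true effect is 0.50 with SD 0.75 and 40 completers per group. What is absent from the protocol text is a detail of analysis that it hands to the SAP. The SAP text was not available here, so its content cannot be called missing. Several contrasts would serve, each with a price, and statisticians would reasonably differ among them.

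The conclusion rests on the SAP fixing the primary contrast before unblinding, and on this being a Phase 2 study for which strict control across doses is not demanded. If the SAP left the choice open and each dose were tested at two-sided 0.10, the chance of at least one false positive would be 17.6% for the two high doses and 23.6% for all three, or 8.8% and 11.8% in the drug's favour. Readers should take the 90% as the power for a single dose with a true effect of 0.50, most plausibly 2.0 or 4.0 mg.
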